### **Aims and hypotheses**

**Primary Aim 1:** To examine whether measuring unattended clinic BP with an automated device will provide a more accurate estimate of awake BP on ABPM than measuring attended clinic BP with an automated device.

**Hypothesis 1a:** The absolute difference with awake BP will be smaller for unattended vs. attended clinic BP.

**Hypothesis 1b:** The agreement between hypertension status using BP measured in the clinic and on ABPM while awake will be higher when clinic BP is measured unattended vs. attended. Also, the prevalence of both white coat and masked hypertension will be lower when measuring unattended clinic BP.

**Primary Aim 2:** To examine whether a new HBPM device provides an accurate approach for measuring sleep BP.

**Hypothesis 2a:** Sleep BP on HBPM will provide an accurate estimate of sleep BP on ABPM.

**Hypothesis 2b:** HBPM will be better tolerated (e.g., less awakening during sleep, pain, bruising) than ABPM.

**Primary Aim 3:** To compare the associations of unattended versus attending clinic BP, unattended clinic BP versus awake BP on ABPM, and sleep BP on HBPM versus ABPM with two markers of end-organ damage, left ventricular mass index (LVMI) and urinary albumin-to-creatinine ratio (ACR).

**Hypothesis 3a:** The association with end-organ damage will be stronger for unattended vs. attended clinic BP.

**Hypothesis 3b:** The association with end-organ damage will be similar for unattended clinic BP and awake BP.

**Hypothesis 3c:** The association with end-organ damage will be similar for sleep BP by HBPM and ABPM.

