#### **Statistical analysis:**

1. Calculate the distribution of the variables in **Table 1**, overall, and separately for participants who were attended then unattended, unattended then attended, as well as participants who underwent ABPM before HBPM, and HBPM before ABPM.
2. Do the following analysis for **Table 2** for those with complete BP data on ABPM, attended, and unattended:
  - a. For awake systolic BP, calculate the mean (with standard deviation) BP on ABPM, attended, and unattended
  - b. Calculate the absolute mean difference with 95% confidence intervals for ABPM vs. attended, ABPM vs. unattended, and attended vs. unattended, using mixed model to determine the difference between the differences.
  - c. Repeat items **2a** and **2b** for awake diastolic BP on ABPM, attended and unattended.

3. Do the following analysis for **Table 3** for those with complete BP data on ABPM, attended, and unattended:
  - a. Calculate the percentage (with 95% confidence interval) of participants with hypertension on awake ABPM (i.e., ABPM\_HYPER = 1)
  - b. Calculate the percentage (with 95% confidence interval) of participants with hypertension on attended BP measurements (i.e., ATTENDED\_HYPER = 1).
  - c. Calculate the percentage (with 95% confidence interval) of participants with hypertension on unattended BP measurements (i.e., UNATTENDED\_HYPER = 1).
  - d. Calculate the percentage (with 95% confidence intervals) of participants with hypertension on attended and awake ABPM (i.e., HYP\_AB\_ATTEND = 1).
  - e. Calculate the percentage (with 95% confidence intervals) of participants with hypertension on unattended and awake ABPM (i.e., HYP\_AB\_UNATTEND = 1).
  - f. Calculate the percentage (with 95% confidence intervals) of participants with white coat hypertension on ABPM and attended BP (i.e., WHIT\_AB\_ATTEND = 1).
  - g. Calculate the percentage (with 95% confidence intervals) of participants with white coat hypertension on ABPM and unattended BP (i.e., WHIT\_AB\_UNATTEND = 1)
  - h. Calculate the percentage (with 95% confidence intervals) of participants with masked hypertension on ABPM and attended BP (i.e., MASK\_AB\_ATTEND = 1).
  - i. Calculate the percentage (with 95% confidence intervals) of participants with masked hypertension on ABPM and unattended BP (i.e., MASK\_AB\_UNATTEND = 1)
4. Do the following analysis for those with complete BP data on ABPM, attended, and unattended:

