  - a. **Table 4**, use a 2 x 2 table to determine the agreement hypertension on ABPM and clinic BP (i.e., HYP\_AB\_ATTEND versus HYP\_AB\_UNATTEND); provide the p-value from kappa statistics.
  - b. **Table 5**, use a 2 x 2 table to determine the agreement white coat hypertension on ABPM and clinic BP (i.e., WHIT\_AB\_ATTEND versus WHIT\_AB\_UNATTEND); provide the p-value from kappa statistics.
  - c. **Table 6**, use a 2 x 2 table to determine the agreement masked hypertension on ABPM and clinic BP (i.e., WHIT\_AB\_ATTEND versus WHIT\_AB\_UNATTEND); provide the p-value from kappa statistics.
5. Do the following analysis for **Table 7** for those with complete sleep BP data on ABPM and HBPM:
  - a. For sleep systolic BP, calculate the mean BP (with standard deviation) on ABPM and HBPM.
  - b. Calculate the absolute mean difference with 95% confidence intervals for ABPM vs. HBPM, using a paired T-test.
  - c. Repeat items 5a and 5b for sleep diastolic BP on ABPM and HBPM.
6. **Table 8**. Calculate the number and percentage of side effects and tolerability (**listed in Table 8**) that occurred in ABPM only, HBPM only, both ABPM and HBPM, and occurred for neither ABPM nor HBPM.
7. **Table 9**. Restrict the analysis to those with complete data on attended and unattended BP and complete data on left ventricular mass index .
  - a. Use linear regression to determine the relationship between attended SBP with left ventricular mass index.
  - b. Repeat the analysis for attended DBP, unattended SBP, unattended DBP with left ventricular mass index, separately.

8. **Table 10.** Restrict the analysis to those with complete BP data on unattended and awake ABPM and complete data on left ventricular mass index.
  - a. Use linear regression to determine the relationship between unattended SBP with left ventricular mass index.
  - b. Repeat the analysis for unattended DBP, awake SBP on ABPM, awake DBP on ABPM with left ventricular mass index, separately.
9. **Table 11.** Restrict the analysis to those with complete sleep BP data on ABPM and HBPM and complete data on left ventricular mass index.
  - c. Use linear regression to determine the relationship between sleep SBP on ABPM with left ventricular mass index.
  - d. Repeat the analysis for sleep DBP on ABPM, sleep SBP on HBPM, and sleep DBP on HBPM with left ventricular mass index, separately.

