Married, %	213 (35.3)	105 (34.9)	108 (35.8)	102 (33.8)	111 (36.9)
Not living alone, %	152 (25.2)	77 (25.6)	75 (24.8)	78 (25.8)	74 (24.6)
Smoking status, %					
Never	509 (84.6)	250 (83.1)	259 (86.0)	260 (86.1)	249 (83.0)
Former	79 (13.1)	44 (14.6)	35 (11.6)	35 (11.6)	44 (14.7)
Current	14 (2.3)	7 (2.3)	7 (2.3)	7 (2.3)	7 (2.3)

Table 1 continued.

Current drinker, %	405 (67.2)	202 (67.1)	203 (67.2)	202 (66.9)	203 (67.4)
Good self-reported sleep quality, %	179 (30.1)	87 (29.4)	92 (30.8)	89 (30.0)	90 (30.2)
Self-reported physical activity per week, %	2.8 (2.0)	2.9 (2.1)	2.8 (2.0)	2.8 (2.1)	2.9 (1.9)
Mean (SD)	3.0 (0.0 - 20.0)	3.0 (0.0 - 20.0)	3.0 (0.0 - 10.0)	3.0 (0.0 - 20.0)	3.0 (0.0 - 10.0)
Median (min - max)					

**Table 2.** Mean difference in awake systolic and diastolic BP, separately, with ABPM vs. attended BP, ABPM vs. unattended BP, and Attended vs. Unattended BP, N=569

	ABPM Mean (SD) Median (min – max)	Attended Mean (SD) Median (min – max)	Unattended Mean (SD) Median (min – max)	Mean difference for ABPM vs. Attended BP (95% CI)	Mean difference for ABPM vs. Unattended BP (95% CI)	Mean difference for Attended vs. Unattended BP (95% CI)	P (difference in differences = 0)
Awake systolic BP	118.7 (10.2) 117.8 (87.6 - 172.8)	119.4 (12.1) 117.8 (92.2 - 179.5)	118.7 (11.9) 117.2 (90.5 - 179.8)	-0.69 (-1.36, -0.03)	-0.004 (-0.64, 0.64)	0.69 (0.39, 0.99)	<.0001
Awake diastolic BP	74.2 (7.0) 73.3 (52.9 - 98.9)	72.7 (7.8) 71.3 (53.5 - 97.7)	72.2 (7.7) 71.0 (47.2 - 98.5)	1.55 (1.08, 2.03)	2.03 (1.55, 2.51)	0.47 (0.25, 0.69)	<.0001

**Table 3.** The prevalence of hypertension by awake ABPM, attended, and unattended BP reading, N=569

Hypertension	Prevalence (95% CI)
ABPM hypertensive range	10.0 (7.7,12.8)
Attended clinic BP in hypertensive range	7.2 (5.2,9.7)
Unattended clinic BP in hypertensive range	14.1(11.3,17.2)
ABPM and attended clinic BP in hypertensive range	4.6 (3.0,6.6)
ABPM and unattended clinic BP in hypertensive range	6.9 (4.9,9.3)
White coat hypertension	
Hypertensive attended clinic BP with normal ABPM	2.6(1.5,4.3)
Hypertensive unattended clinic BP with normal ABPM	7.2 (5.2,9.7)
Masked hypertension	
Hypertensive ABPM with normal attended clinic BP	5.5 (3.7,7.6)
Hypertensive ABPM with normal unattended clinic BP	3.2 (1.9,5.0)

Hypertension will be defined as:

Awake ABPM readings  $\geq$ 135 or 85 mm Hg

Attended: SBP/DBP readings  $\geq$ 140 or 90 mm Hg

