**D.11.4.2. Hypothesis 1b: The agreement between hypertension in the clinic and awake hypertension will be higher for unattended versus attended clinic BP.** Also, the prevalence of both white coat and masked hypertension will be lower when BP is measured unattended versus when it is measured

**attended in the clinic.** Using the first three clinic BP measurements obtained at each visit and awake BP from ABPM, we will calculate the prevalence of clinic hypertension, based on unattended and attended measurements separately, and awake hypertension. We will calculate overall agreement and agreement above that expected by chance alone (i.e., the Kappa statistic) between (1) clinic hypertension, measured attended, and awake hypertension and (2) clinic hypertension, measured unattended, and awake hypertension. We will calculate the prevalence of white coat hypertension and masked hypertension defined using unattended and attended clinic BP, separately, and awake BP from ABPM. The statistical significance of the differences in these statistics when BP is measured unattended versus attended will be calculated using McNemar tests and bootstrapping techniques as these measures are not independent.

**D.11.5. Aim 2. Test whether a new HBPM device provides an accurate approach for measuring sleep BP.** We will calculate the characteristics of participants randomized to have their sleep BP measured by (1) ABPM then HBPM or (2) HBPM then ABPM. The statistical significance of differences across the randomization assignments will be calculated using t-tests and chi-square tests, as appropriate.

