**D.12. Sample size/minimum detectable effects.**

[figure not shown]
**D.12.1. Aim 1.** Sample size and minimal detectable difference calculations were based on 80% statistical power and a two-sided alpha level of 5%. These calculations were performed using simulations and R version

3.3.2. We estimate that a sample size of 600 participants (630 enrolled participants with 30 participants [5%] not completing the study) will allow us to detect small but clinically relevant differences for each aim.

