#### D.12.1.1. Sample size considerations for hypothesis 1a.

**Figure 4** shows the minimal detectable difference in differences with awake ABPM comparing unattended vs attended clinic BP. With 600 participants we can detect that the absolute difference with awake ABPM is 1.5 and 1.2 mm Hg smaller for unattended vs attended clinic BP assuming a correlation of 0.5 and 0.7, respectively between clinic BP and awake BP on ABPM. In a sub-group of 160 participants (e.g., African Americans), we can detect that the absolute difference with awake ABPM is 3.1 and 2.4 mm Hg smaller for unattended vs. attended clinic BP.

Smaller absolute differences can be detected if the correlation between attended and awake BP is higher.

**D.12.1.2. Sample size considerations for hypothesis 1b.** If 85% of participants have the same concordance/discordance status for both comparisons (i.e., attended clinic hypertension versus awake hypertension and unattended clinic hypertension versus awake hypertension), enrollment of 600 participants will provide 80% statistical power to detect a difference of 5% in the two overall agreements (e.g., 70% vs. 75%). If the expected agreement is 50%, we will have an 80% statistical power to detect a difference between Kappa statistics of 0.4 and 0.5 using a two-sided alpha level of 0.05. With 600 participants and a phenotype prevalence of 15%, we can detect a difference in the prevalence of 4% when clinic BP is measured unattended versus attended. In a sub-group of 160 participants, we can detect a difference of 8%. Based on these estimates, we chose to enroll 630 participants in the proposed study (n=600 with complete data).

#### D.12.2. Aim 2

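### Analysis Plan item 3 and Tables 3 to 6 omit the paired comparison of white coat and masked prevalence that D.11.4.2 specifies for Hypothesis 1b

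*Combined protocol and SAP*

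**What the plan says.** The Analysis Plan restates Hypothesis 1b, under Primary Aim 1, as a directional, within-person claim: "the prevalence of both white coat and masked hypertension will be lower when measuring unattended clinic BP".

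Its Statistical analysis items 3f to 3i then ask for four separate prevalences, each with its own interval; item 3h reads "Calculate the percentage (with 95% confidence intervals) of participants with masked hypertension on ABPM and attended BP". Items 4a to 4c cross-tabulate the attended and unattended phenotypes and instruct the analyst to "provide the p-value from kappa statistics".

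The filled tables follow that text. Table 3, titled "The prevalence of hypertension by awake ABPM, attended, and unattended BP reading, N=569", lists each prevalence with an interval and has no difference or P column. Tables 4 to 6 print the paired cells and a kappa. Tables 2 and 7, which are also within-person comparisons, do report differences with P-values.

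The research plan differs. D.11.4.2 says that the significance of differences between unattended and attended results "will be calculated using McNemar tests and bootstrapping techniques as these measures are not independent". D.12.1.2 sizes this contrast: a 4-point difference at 15% prevalence with 600 participants.

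**The concern.** Both prevalences come from the same 569 people, and most people are classified alike by both methods. Single-sample intervals ignore that pairing and are too wide for judging the difference. A kappa test asks whether agreement exceeds chance. It can be overwhelmingly significant whether prevalence rises, falls or stays the same under the second method.

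So no step in the Analysis Plan produces an estimate or test of the prevalence statement in Hypothesis 1b. At stake is whether the masked component is read as unresolved when the paired data point one way, and whether the size of the white coat shift is reported at all.

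**Working it through.** **Inputs.** N = 569 (Tables 3 to 6). Discordant cells, attended only against unattended only:
- Table 6, masked: 14 and 1.
- Table 5, white coat: 0 and 26.
- Table 4, hypertensive on both ABPM and clinic BP: 1 and 14.

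**Step 1. Reproduce the plan's figures.** Exact (Clopper-Pearson) limits on the table margins give:

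| Phenotype | Attended | Unattended |
|---|---|---|
| Masked | 31/569 = 5.45% (3.73, 7.64) | 18/569 = 3.16% (1.89, 4.95) |
| White coat | 15/569 = 2.64% (1.48, 4.31) | 41/569 = 7.21% (5.22, 9.65) |

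These match Table 3 to rounding, so its intervals are single-sample. The kappas also reproduce: 0.756, 0.517 and 0.681, against 0.76, 0.52 and 0.68 in Tables 4 to 6.

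**Step 2. What the planned outputs convey.** The masked intervals overlap from 3.7 to 5.0. Treating the two samples as independent gives p = 0.057 and a 95% CI for the difference of -4.64 to +0.07. The kappa tests against zero agreement give z = 16.9 (masked) and z = 14.1 (white coat), although the two prevalences move in opposite directions.

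**Step 3. Paired analysis.** With b = attended only and c = unattended only:
- difference = (c - b)/N
- SE = sqrt[(b + c) - (b - c)²/N]/N
- exact McNemar p = 2 × P(X ≤ min(b, c)), with X binomial (b + c, 0.5).

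Masked: (1 - 14)/569 = -2.28 points. SE = sqrt(15 - 169/569)/569 = 0.674 points. 95% CI -3.61 to -0.96 (bootstrap -3.69 to -1.05). Exact p = 2 × (1 + 15)/2^15 = 0.001; continuity-corrected p = 0.0019.

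White coat: 26/569 = +4.57 points. SE = sqrt(26 - 676/569)/569 = 0.875 points. 95% CI 2.85 to 6.29 (bootstrap 2.99 to 6.33). Exact p = 2 × 0.5^26 = 3.0e-8.

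Clinic hypertension, adding Tables 4 and 5: attended only 1 + 0 = 1, unattended only 14 + 26 = 40. Difference 39/569 = +6.85 points. SE = sqrt(41 - 1521/569)/569 = 1.088 points. 95% CI 4.72 to 8.99. Exact p = 2 × (1 + 41)/2^41 = 4e-11.

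**Step 4. Which readings the tables use.** D.11.4 bases the primary analysis on the first three readings at Visits 1 and 2. Because the order reverses at Visit 2, that is three readings per method per person. A mean of three whole numbers, to one decimal, ends in .0, .3 or .7. Table 1 has attended and unattended systolic extremes of 92.2, 95.2, 179.5 and 179.8. These fit 553/6, 571/6, 1077/6 and 1079/6. The results packet in the manual also averages six readings per method.

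**Step 5. What the contrast measures.** The Data management section defines attended hypertension at 140/90 and unattended at 135/85 mm Hg, as does Table 6 of the research plan. Suppose a person's two clinic values were identical. The lower unattended cut-off would then place every discordant pair on one side: masked on attended only, white coat on unattended only. The observed 14 against 1 and 0 against 26 are close to that pattern, while mean BP differs between methods by only 0.69 mm Hg systolic and 0.47 mm Hg diastolic (Table 2).

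**The case against.** The test is not absent from the file. D.11.4.2 still specifies it, so a reader who infers that half of a primary hypothesis was left without any planned test goes too far. What the documents show is an Analysis Plan, with its filled tables, that leaves out a comparison the research plan requires.

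Nor is a reader confined to comparing intervals. Tables 5 and 6 print the full paired cells, and every p-value above comes from them. The Analysis Plan never says to judge the hypothesis by overlap. The misleading appearance is also limited to masked hypertension: the white coat intervals (1.5 to 4.3 and 5.2 to 9.7) do not overlap. Since the hypothesis says both prevalences will be lower, Table 3 alone shows that the joint statement fails, and no masked result can rescue it.

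All of this stands, and it lowers the stakes. It does not supply the missing estimate and test for each component, and it leaves two analysis texts in one file that disagree.

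It might also be objected that tests added once the tables are filled are post hoc. That carries little weight for McNemar and bootstrap, which D.11.4.2 already specifies. It does apply to the choice of readings and to any new sensitivity analysis.

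**Conclusion.** The concern holds in a limited form. Items 3f to 3i and Tables 3 to 6 omit the paired comparison of D.11.4.2, and neither separate intervals nor kappas can stand in for it. For masked hypertension the omission changes what a reader would conclude: overlapping intervals, against a paired difference of -2.28 points (-3.61 to -0.96). For white coat hypertension it withholds the size and test of a shift that is already visible, +4.57 points (2.85 to 6.29), contrary to the hypothesis.

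Two stronger inferences are not supported. First, these p-values are not the D.11.4.2 results: they apply to the tables as printed, which appear to rest on six-reading means. Second, p = 0.001 does not show that unattended measurement lowers masked prevalence. The contrast combines the method with a lower cut-off, and the one-sided discordance is largely what that cut-off alone would produce. The printed tables cannot separate the two.

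**What to change.** 1. In item 3, for clinic, white coat and masked hypertension, add the paired difference (unattended minus attended), a paired or bootstrap 95% CI and the McNemar p-value. Add matching columns to Table 3, and base the prevalence statement for Hypothesis 1b on them.
2. Run this on the first-three-readings basis of D.11.4. Otherwise, reconcile which readings are primary, on grounds independent of the results, and show the other set as a sensitivity analysis. State in each table which readings are averaged.
3. State that the contrast combines measurement method with different cut-offs. Add a sensitivity analysis that applies one threshold to both methods (for example each of the plan's two clinic cut-offs in turn), labelled as added after the tables were produced. Attribute no difference to unattended measurement before it is reported.
4. Correct item 4c, which names the white coat variables for the masked table. The printed Table 6 margins (31 and 18) match masked hypertension, so the slip is in the text.

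The cost is a few lines of text and code. The three-reading and common-threshold runs need the individual readings, which the visit forms already collect; no new data are required.

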### **Your blood pressure measurements:**

Attended Blood Pressure*	Unattended Blood Pressure*
Systolic Blood Pressure: _____ mmHg	Systolic Blood Pressure: _____ mmHg
Diastolic Blood Pressure: _____ mmHg	Diastolic Blood Pressure: _____ mmHg
Heart Rate: _____ beats per minute	Heart Rate: _____ beats per minute

\*Average of six blood pressure measurements.

**Based on 2017 guidelines from the American College of Cardiology and American Heart Association, categories of clinic blood pressure are defined as follows:**

Blood Pressure Category	Systolic Blood Pressure		Diastolic Blood Pressure
Normal	<120 mm Hg	and	<80 mm Hg
Elevated	120-129 mm Hg	and	<80 mm Hg
Hypertension			
Stage 1	130-139 mm Hg	or	80-89 mm Hg
Stage 2	≥140 mm Hg	or	≥90 mm Hg

This is based on average of the blood pressure readings taken during your first two clinic visits.

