#### **Data management:**

Create the following variables to define hypertension:

1. Create the variable ABPM\_HYPER by assigning 1 to those with mean awake ABPM  $\geq 135$  mm Hg (systolic BP) or 85 mm Hg (diastolic BP) and 0 if otherwise.
2. Create the variable ATTENDED\_HYPER by assigning 1 to those with mean attended BP  $\geq 140$  mm Hg (systolic BP) or 90 mm Hg (diastolic BP) and 0 if otherwise.
3. Create the variable UNATTENDED\_HYPER by assigning 1 to those with mean unattended BP  $\geq 135$  mm Hg (systolic BP) or 85 mm Hg (diastolic BP) and 0 if otherwise.
4. Identify the following individuals:
  1. HYP\_AB\_ATTEND should equal 1 if ABPM\_HYPER = 1 and ATTENDED\_HYPER = 1, and 0 if otherwise.
  2. HYP\_AB\_UNATTEND should equal 1 if ABPM\_HYPER = 1 and UNATTENDED\_HYPER = 1, and 0 if otherwise.
  3. WHIT\_AB\_ATTEND should equal 1 if ABPM\_HYPER = 0 and ATTENDED\_HYPER = 1, and 0 if otherwise.
  4. WHIT\_AB\_UNATTEND should equal 1 if ABPM\_HYPER = 0 and UNATTENDED\_HYPER = 1, and 0 if otherwise.
  5. MASK\_AB\_ATTEND should equal 1 if ABPM\_HYPER = 1 and ATTENDED\_HYPER = 0, and 0 if otherwise.
  6. MASK\_AB\_UNATTEND should equal 1 if ABPM\_HYPER = 1 and UNATTENDED\_HYPER = 0, and 0 if otherwise.

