**D.11.3. Exploratory statistics comparing unattended and attended BP.** We will calculate characteristics of participants by randomization assignment: unattended then attended clinic BP measurement or attended then unattended clinic BP measurement at the first visit. Scatterplots will be assembled to show the relationship between unattended clinic BP versus awake BP and attended clinic BP versus awake BP. For each comparison, intraclass correlation coefficients will be calculated. The statistical significance of the difference in the correlation coefficients will be calculated using the Fisher r-to-z transformation accounting for the correlation between attended and unattended clinic BP. We will also assemble Bland-Altman plots showing the differences between unattended and attended BP, separately, versus awake BP on ABPM.

**D.11.4. Aim 1. Test whether measuring unattended clinic BP with an automated device will provide a more accurate estimate of awake BP on ABPM than measuring attended clinic BP with an automated device.** Our primary analyses for Hypothesis 1 will be tested using the first three clinic BP measurements obtained at Visits 1 and 2. In sensitivity analyses, we will use the fourth through sixth BP measurements from these visits. Separate analyses will be performed for SBP and DBP.

**D.11.4.1. Hypothesis 1a: The absolute difference with awake BP will be smaller for unattended vs. attended clinic BP.** The absolute difference between mean unattended clinic BP and awake BP and mean attended clinic BP and awake BP, separately, will be calculated. We will test whether these differences are statistically significantly different from zero using paired t-tests. Next, we will determine whether the absolute difference between unattended clinic BP and awake BP is smaller than the absolute difference between attended clinic BP and awake BP by calculating if the difference in differences (i.e., absolute difference between unattended clinic BP and awake BP minus the absolute difference between attended clinic BP and awake BP) is less than zero using a paired t-test. If the absolute differences between unattended and attended clinic BP and awake BP differs by randomization assignment, we will use a mixed model with randomization assignment as a covariate. This analysis will be performed in the overall population and in sub-groups defined by age (categorized in tertiles), race/ethnicity (white, African American, Hispanic) and sex.

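### The kappa of 0.76 in SAP Table 4 is not clinic-versus-ABPM agreement, and no SAP item delivers the agreement comparison planned for Hypothesis 1b

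*Combined protocol and SAP*

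**What the plan says.** The SAP restates Hypothesis 1b under Aims and hypotheses. Under Data management ("Create the following variables to define hypertension") it defines ABPM_HYPER, ATTENDED_HYPER and UNATTENDED_HYPER, then composites of these. HYP_AB_ATTEND is 1 only if awake ABPM and attended BP are both raised, and HYP_AB_UNATTEND is the unattended counterpart.

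Under Statistical analysis, item 4a tells the analyst to "use a 2 x 2 table to determine the agreement hypertension on ABPM and clinic BP" by crossing HYP_AB_ATTEND with HYP_AB_UNATTEND and giving the p-value from kappa. Table 4 carries that label and prints kappa 0.76. Items 4b and 4c have the same form for white coat (Table 5) and masked hypertension (Table 6). Item 4c names the white coat variables.

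Protocol D.11.4.2 plans something else: overall agreement and kappa between ("1) clinic hypertension, measured attended, and awake hypertension and (2) clinic hypertension, measured unattended, and awake hypertension"). Differences in agreement, kappa and phenotype prevalence between methods "will be calculated using McNemar tests and bootstrapping techniques as these measures are not independent". D.12.1.2 includes among its justifications that "we will have an 80% statistical power to detect a difference between Kappa statistics of 0.4 and 0.5", on the condition that expected agreement is 50%. D.11.4 states: "Our primary analyses for Hypothesis 1 will be tested using the first three clinic BP measurements obtained at Visits 1 and 2".

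**The concern.** Hypothesis 1b needs awake ABPM as one margin of each agreement table. In Table 4 it is never a margin, because it is a condition built into both. Someone with normal ABPM is No on both variables whatever the clinic readings were, so clinic false positives count as agreement and cannot lower kappa. The requested p-value would test whether that concordance exceeds chance. It would not test whether unattended BP agrees with ABPM better than attended BP does.

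Two things are at stake. The table title invites a reader to take 0.76 as clinic-versus-ABPM agreement. The agreement half of a primary-aim hypothesis, which contributed to the sample size justification, is left without its planned statistic or test.

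**Working it through.** **Printed kappas.** kappa = (po - pe)/(1 - pe), where po is observed and pe is chance-expected agreement. Cells are in the order yes/yes, attended only, unattended only, no/no, N=569.

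- Table 4 (25, 1, 14, 529): po = 554/569 = 0.9736; pe = (26×39 + 543×530)/569² = 0.8920; kappa = 0.756 (printed 0.76).
- Table 5 (15, 0, 26, 528): kappa = 0.517 (printed 0.52).
- Table 6 (17, 14, 1, 537): kappa = 0.681 (printed 0.68).

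**Joint counts.** Table 4 gives the ABPM-hypertensive cells with at least one clinic positive, and Table 6 gives the 17 masked by both methods. Table 5 gives the ABPM-normal cells with at least one clinic positive. The remainder is 569 - 57 - 41 = 471.

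| Awake ABPM | Both clinic methods raised | Attended only | Unattended only | Neither | Total |
|---|---|---|---|---|---|
| Hypertensive | 25 | 1 | 14 | 17 | 57 |
| Normal | 15 | 0 | 26 | 471 | 512 |

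The margins agree with Table 3: ABPM 57/569 = 10.0%, attended 41/569 = 7.2%, unattended 80/569 = 14.1%.

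**What the gating does.** Table 4's No/No cell is 529 = 512 + 17, so 512 of the 529 are there by definition. Among the 57 who could be classified either way (25, 1, 14, 17), kappa is 0.490. Table 6 restricted to the same 57 is that table with the labels reversed, so it is also 0.490, against 0.68 as printed. Table 5 is barely affected: 0.515 among the 512 ABPM-normal against 0.517 overall. Plain attended-versus-unattended clinic hypertension, ignoring ABPM (40, 1, 40, 488), has kappa 0.63.

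**The statistics D.11.4.2 plans.** Cells are both raised, clinic only, ABPM only, neither.

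- Attended v awake (26, 15, 31, 497): po = 523/569 = 91.9%; pe = (41×57 + 528×512)/569² = 0.842; kappa = 0.488.
- Unattended v awake (39, 41, 18, 471): po = 510/569 = 89.6%; pe = (80×57 + 489×512)/569² = 0.787; kappa = 0.512.
- From 20,000 multinomial bootstrap draws of the joint table, 95% intervals are 0.354 to 0.608 (attended), 0.400 to 0.616 (unattended), and -0.087 to 0.141 for the difference, 0.5123 - 0.4877 = 0.025.
- Overall agreement, unattended minus attended: (510 - 523)/569 = -2.3 points (bootstrap interval -4.6 to 0.0). Attended alone is right for 1 + 26 = 27 participants and unattended alone for 14 + 0 = 14; exact McNemar p = 0.06.

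The errors trade off. Unattended BP detects 39 of 57 ABPM hypertensives against 26 of 57 attended, but correctly clears 471 of 512 ABPM-normals against 497 of 512.

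**The prevalence half of 1b.** White coat: 15 attended v 41 unattended, discordant 0 v 26, exact McNemar p = 3×10⁻⁸, against the hypothesis. Masked: 31 v 18, discordant 14 v 1, p = 0.001, in its favour. The SAP tests neither.

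**Item 4c.** Table 6's margins of 31 and 18 are the masked counts, so the white coat variable names look clerical.

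**Reading set.** Clinic order is reversed at Visit 2, so the first three readings at each visit supply three readings per method in total. Means of three whole numbers end in .0, .3 or .7. Table 1 prints extremes of 92.2, 90.5, 179.8 and 47.2, which are impossible for three readings and possible for six. The participant results sheet likewise reports an "Average of six blood pressure measurements". The printed means therefore appear to use all six readings per method.

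**The case against.** SAP Objective 3 speaks loosely of agreement between hypertension phenotypes on ABPM and clinic BP, and items 4a to 4c can be read as serving it. Table 4's row and column headings do name the composites (for example "ABPM and unattended clinic BP in hypertensive range"), so an attentive reader could see what was crossed. The missing kappas follow exactly from the printed tables, nothing is lost, and no conclusion in the documents rests on 0.76. The kappa power figure is one of three calculations given for 1b. The rebuilt tables also have expected agreement of about 0.84 and 0.79, well away from the assumed 50%.

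These points are accurate, and they limit the claim in three ways. The gap is in specification and reporting, with the data intact. The 0.76 is best described as concordance of ABPM-gated composites, since the ungated figure is 0.63. A reader could be misled, though not inevitably. None of this supplies the missing analysis: the same SAP restates Hypothesis 1b, and none of its items 1 to 12 specifies either clinic-versus-awake kappa, their difference or a paired test.

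**Conclusion.** The concern holds and must be fixed. Followed as written, the SAP produces a mislabelled statistic of 0.76 where the clinic-versus-awake kappas are 0.49 and 0.51, and it leaves the agreement part of Hypothesis 1b untested. On the printed counts that part is inconclusive.

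The size rests on the classifications tabulated in the SAP. These appear to come from six-reading means, so the values could differ from the D.11.4 primary analysis. That Tables 3 to 6 use the same means as Tables 1 and 2 is inferred. The prespecified cut-points also differ (140/90 attended, 135/85 unattended), so the trade-off in errors and the white coat and masked contrasts reflect cut-point as well as attendance.

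**What to change.** - Replace item 4a with two 2×2 tables: ATTENDED_HYPER by ABPM_HYPER and UNATTENDED_HYPER by ABPM_HYPER. Report overall agreement and kappa for each, the kappa difference with a participant-level bootstrap interval, and a McNemar test of agreement, as D.11.4.2 plans.
- Keep Tables 5 and 6, relabelled as paired attended-versus-unattended tables. Test white coat and masked prevalence with McNemar in place of the kappa p-value.
- Correct item 4c to the MASK variables.
- Run the primary version on the first three readings at each visit, as D.11.4 states, or state and justify the use of all six.
- Optionally, add a sensitivity analysis at one common clinic cut-point.

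The cost is SAP wording and a few lines of code on existing data, with no new data collection. The 0.76 would no longer be presented as clinic-versus-ABPM agreement.
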